Virtual reality (VR) has expanded in recent years from the personal entertainment industry to the medical field. It has been found in preliminary study to be safe and effective as an adjunct to standard sedative and analgesic protocols in reducing pain and anxiety for patients undergoing upper gastrointestinal endoscopy, dental procedures, dressing changes for burns, and major orthopedic surgical cases (Vazquez 2017, Furman 2009, Morris 2009, Chan 2017). To date, the use of VR during hand and wrist surgery has not been studied to reduce intraoperative anesthetic requirements and improve the postoperative patient experience. A positive result from the proposed study could lead to a change in practice, with the introduction of a non-pharmacologic, patient-led intervention, potentially reducing the burden of unnecessary oversedation while providing a satisfactory perioperative experience.

B3. DESCRIPTION OF RESEARCH PROTOCOL

A. Study Design – Overview, Methods, Procedures

Study Overview

The proposed study is a randomized, controlled trial to evaluate the effectiveness of VR as an adjunct to standard anesthetic practice for hand and wrist surgery. Patients will be randomized to undergo immersion relaxation via the use of VR during their procedure or control. In both groups patients will undergo regional anesthesia preoperatively according to standard practice. Patients will then be assessed postoperatively to assess the intraoperative propofol dose between groups, as well as secondary outcomes including patient satisfaction.

Study Procedures

Patients who meet inclusion criteria with no exclusions will be approached to provide written informed consent in the perioperative period, as detailed below (Section B6). At this time we will provide patients with a study handout to ensure complete understanding of the study (see attached). We will also ask participants to complete a brief survey about how they are feeling at baseline (see attached). This should take about five minutes to complete.

After consent and prior to surgery, patients will be randomized in a 1:1 allocation to either intraoperative VR or usual care control. Given the nature of the intervention, we are unable to blind treatment allocation.

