In both groups patients will undergo regional anesthesia preoperatively according to standard practice. Patients in the VR group will undergo immersion relaxation via the use of a VR headset and software packages for their intraoperative course as an adjunct to standard anesthesia practice. Control patients will undergo usual anesthesia care as determined by their anesthesia provider, without the addition of the VR device. All intraoperative anesthetic management and medication administration will be at the discretion of the treating provider. Patients will be monitored (vital signs, capnography) according to ASA standards for a MAC anesthetic. This data will be passively abstracted from the medical record in order to assess study outcomes.

It is possible that by virtue of being enrolled in this study participants may receive fewer medications than they would otherwise receive if they did not participate. For example, an anesthesia provider may not administer the initial bolus of pre-procedure propofol for a patient in the VR group, but instead continue to monitor them and only administer it if/when needed clinically. This potential for divergence from the standard process is well within clinically acceptable standards of care, but has been described as a potential risk associated with participation. In both groups patients will be monitored by their anesthesiologist, assessed and treated as necessary. The assessment is conducted by the clinical anesthesiologist independent of their participation in the study or study group assignment.

Intervention: Virtual Reality Immersive Relaxation

The intervention to be studied in the proposed trial is a relaxing, immersive virtual reality environment. Immersion takes place by wearing a VR headset connected to a software platform on an iPad. There are various environments that have been created with VR software, all designed to promote relaxation and calmness. Examples include sitting in a canoe on a river, a peaceful meadow or forest, or sitting on a mountaintop. To ensure comfort with the VR setting, patients in the intervention group will be allowed to select from one or several of the prespecified intraoperative relaxation packages, consistent of programs such as those mentioned above.

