PACU stay, as well as postoperative analgesia administration and pain scores. In addition, study team members will review the patients' medical records to collect demographic data and surgical characteristics including intraoperative vital signs, medication administration, and postoperative outcome data. Postoperative pain scores (i.e. 'Rate your pain on a scale from 0 to 10') are documented routinely as part of standard postoperative clinical care, and will be recorded at admission to the PACU and at PACU discharge. Additional baseline characteristics including but not limited to age, race, gender, BMI and comorbidities will be abstracted from the medical record. REDCap will be utilized for survey administration, data collection and storage.

Safety Monitoring and Reporting

This patient population is undergoing surgery and it is expected that they may have a number of unrelated adverse health events during their hospital course. Therefore, we will limit the scope of AE monitoring and reporting to the following:

- All Serious Adverse Events believed to be related to the study procedures
- All non-serious Adverse Events believed to be related to the study procedures

Adverse events will be monitored until the time of PACU discharge.

B. Statistical Considerations

Sample Size Justification: Using a two sided α of 0.05, 80% power, and mean propofol doses of 0.069 (standard deviation 0.03) and 0.042 (SD 0.021), we anticipate needing to enroll a total of 32 patients to be able to detect a 50% reduction in the mean total intraoperative propofol dose. We believe this to be a reasonable effect size given preliminary data from a related study in which investigators were able to demonstrate a >50% reduction in dose for major joint surgery (Chan 2017). In order to compensate for anticipated drop out, we will plan to enroll an additional 8 patients to bring the total planned enrollment to 40 patients, with 20 in each of the two groups.

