It is possible that by virtue of being enrolled in this study participants may receive fewer medications than they would otherwise receive if they did not participate. Risks associated with receiving less propofol include additional movement of the arm, temporary pain or discomfort during surgery, as well as the potential to experience discomfort or anxiety related to being alert in the operating room. If a patient experiences any pain or discomfort, the procedure will be temporarily paused and a local anesthetic injection can be administered. Of note, all patients will receive a nerve block as part of the standard of care for this surgery, regardless of study participation. This nerve block, when properly performed, renders the operative arm insensate and unable to move. Therefore, patients would only experience pain if this block was inadequate, further limiting the risk of experiencing pain. Additionally, participants will be monitored throughout the procedure by the clinical team. Need for additional medications will be consistently assessed throughout surgery, with assessment occurring independently of study participation and in the manner in which the response to surgical stimulation is usually assessed in standard anesthesia practice. .

As with any research study, there is the potential risk of a breach of confidentiality. To minimize the risk of dissemination of health information, all PHI from screening and enrollment will be saved on BIDMC research servers and only coded

information will be included in the REDCap database so as to prevent any unintended dissemination of PHI. No identifiable health information will be exchanged between the VRHealth company and the investigators.

We believe these risks to be outweighed by the benefit of knowledge gained about strategies that could potentially avoid unnecessary oversedation that can sometimes occur with MAC anesthesia.

B6. RECRUITMENT AND CONSENT PROCEDURES

Recruitment

Eligible patients will be identified by operative scheduling lists, surgical clinic visit schedules, and pre-admission testing (PAT) clinic visit scheduling lists. All patients who meet inclusion criteria with no exclusions will be approached in private areas for full written informed consent.

Consent

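### Adverse events filtered by believed relatedness cannot be compared between arms, and intraoperative movement, pain events and pauses are not named as collected data in either arm

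*Combined protocol and SAP*

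**What the plan says.** B3.A, Safety Monitoring and Reporting, expects many unrelated health events in a surgical population and draws this consequence: "Therefore, we will limit the scope of AE monitoring and reporting to the following". Two classes follow: "All Serious Adverse Events believed to be related to the study procedures" and "All non-serious Adverse Events believed to be related to the study procedures". The window is short: "Adverse events will be monitored until the time of PACU discharge". The section does not say who judges relatedness, or whether lighter sedation counts as a study procedure.

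B3.A, Study Procedures, states: "Given the nature of the intervention, we are unable to blind treatment allocation". On the comparator it says: "Control patients will undergo usual anesthesia care as determined by their anesthesia provider, without the addition of the VR device".

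B5 describes what lighter sedation may cost: "Risks associated with receiving less propofol include additional movement of the arm, temporary pain or discomfort during surgery", and also discomfort or anxiety from being alert. If pain or discomfort occurs, "the procedure will be temporarily paused and a local anesthetic injection can be administered".

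Other data are planned for all patients with no relatedness filter. B3.A (Data Collection) lists abstracted intraoperative vital signs and medications, postoperative analgesia, and pain scores at PACU arrival and discharge. B3.B (Secondary Outcomes) lists a postoperative survey whose areas include pain, anxiety and nausea.

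**The concern.** The filter applies to monitoring as well as reporting, so an event not believed related need not be recorded at all. A control patient has almost nothing in the operating room to which an event could be related. In the VR arm, whoever decides knows the assignment. The recorded counts then reflect opinion about cause as well as how often events happened.

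This matters because of the primary outcome. Total propofol dose is set by a provider who knows the arm, and B3.A itself gives the example of a provider holding back the initial bolus in a VR patient. The dose can therefore fall through provider behavior alone. The B1 hypothesis is narrower: it concerns the dose needed for relaxation and comfort. Telling the two apart requires knowing, in both arms, how patients tolerated the operation. A lower dose reached with more movement, pain or interruptions would not be the hypothesized result.

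**Working it through.** The plan states no figure for adverse events, so there is none to reproduce. The only design number used is the arm size in B3.B: 32 + 8 = 40 patients, 40 / 2 = 20 per arm.

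**Step 1. Where could each B5 event be recorded?**

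| B5 event or response | Safety log | Other source planned in both arms | What is left |
|---|---|---|---|
| Arm movement | only if believed related | none named | not named as collected |
| Intraoperative pain or discomfort, as an event | only if believed related | survey (pain); PACU pain scores | both taken after surgery; no record of the event |
| Pause of the procedure | only through a related event | none named | not named as collected |
| Local anesthetic injection | only through a related event | abstracted medications, if charted | partial; no comparison by arm is listed |
| Discomfort or anxiety from being alert | only if believed related | survey (anxiety) | partial; taken after surgery, patients unblinded |

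The lists in B3.A are open-ended, so movement and pauses are not ruled out. They are just not named.

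**Step 2. What does the filter do to counts?** All rates here are assumed. Expected recorded count = 20 × true rate × proportion judged related.

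- Equal true rates of 30%: 20 × 0.30 = 6 events occur in each arm. With 80% judged related in VR and 20% in control, the log shows 20 × 0.30 × 0.80 = 4.8 versus 20 × 0.30 × 0.20 = 1.2.
- Low end, true rate 20%, with 50% and 10% judged related: 20 × 0.20 × 0.50 = 2.0 versus 20 × 0.20 × 0.10 = 0.4.
- High end, true rate 40%, with 80% and 0% judged related: 20 × 0.40 × 0.80 = 6.4 versus 0.
- Opposite direction, with a real excess of 40% versus 10%: 20 × 0.40 = 8 versus 20 × 0.10 = 2 events occur. If 10% of VR events and no control events are judged related, the log shows 8 × 0.10 = 0.8 versus 2 × 0 = 0.

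The filter can create a difference or hide one, depending on how cause is judged.

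**Step 3. What could complete recording show?** Exact power of the two-sided Fisher test at 0.05, 20 versus 20, by enumeration over all outcomes (assumed rates):

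| True rates | Power |
|---|---|
| 5% vs 20% | 17% |
| 10% vs 30% | 24% |
| 10% vs 40% | 49% |
| 10% vs 50% | 74% |

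Even complete recording would usually detect only large differences. Its value is an undistorted description.

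**The case against.** The limit is deliberate and reasoned. Collecting every unrelated event in a surgical population yields noise, and B5 regards the device as non-invasive and of minimal risk. That justifies not recording everything. It does not justify leaving out a short list that the plan itself names.

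The strongest objection is that other data fill the gap, and part of it stands. A reader might infer that the harms of lighter sedation cannot be compared between arms at all. The documents do not support that: the survey, PACU scores and abstracted medications carry no relatedness filter and cover both arms. The postoperative survey items are not in the text, so one cannot assume that they miss intraoperative discomfort. These sources remain partial, because the survey is framed as satisfaction and both it and the PACU scores come after the operation. None of them is stated to record movement or pauses.

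A reader might also infer that VR-arm pain or movement would go uncounted. That is not established. B3.A and B5 link reduced medication to enrollment in the study, which would support a judgment of related. B5 also says that pain would arise only if the block were inadequate, which supports the opposite. The text leaves the matter open.

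Finally, a reader might expect a false-positive safety test, for instance on nausea. No between-arm adverse event analysis is planned, the survey already covers nausea in both arms, and B5 does not list nausea among the risks of less propofol.

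**Conclusion.** The concern holds in limited form. Adverse event records collected under the stated rule should not be read as a comparison of arms. This follows from three stated features: the relatedness filter on monitoring, open allocation, and a control arm with no intraoperative study procedure. Separately, arm movement, intraoperative pain or discomfort as an event, and pauses are not named as collected data in either arm. Pain, anxiety, nausea and rescue injection have partial two-arm coverage.

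The size of the distortion cannot be estimated from the documents. Under the equal-rate assumptions examined (true rates 20% to 40%, with 50% to 80% of VR events and 0% to 20% of control events judged related), expected recorded counts are 2.0 to 6.4 of 20 for VR and 0 to 1.6 of 20 for control.

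The test of the primary outcome is unaffected. What is weakened is its interpretation: a lower dose cannot be fully read as one that kept patients comfortable. The change is worth making because it is cheap.

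**What to change.** Keep the relatedness filter for IRB reporting. In addition, name the B5 items as data to be recorded in every patient, whatever the believed cause: arm movement, intraoperative pain or discomfort, pause of the procedure, and local anesthetic injection. State one method of recording for both arms. This matters because study team members are available in the operating room to help with the device, and extra observation in the VR arm alone would bring back the imbalance. Tabulate the items by arm, with counts and proportions, next to the primary result, and label the table descriptive.

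The cost is a few fields added to the chart abstraction already planned. Movement and pauses may be charted unevenly, and direct observation would be more complete but cost more. At 20 per arm only large differences are likely to be detected, so the absence of a visible difference must not be presented as evidence of equal tolerance. The change affects data capture only and alters no clinical care.

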During their operation, after appropriate positioning has been taken place, the patient will don the VR headset and view the programming of their choice. Study team members will be available intraoperatively to assist with the implementation of the device programming. The relaxation programming will run for the duration of the operative procedure. At any time, the patient or anesthesia provider can decline to continue with the VR programming. At the end of the procedure the VR headset will be removed and standard postoperative care will commence.

Control Group

Subjects in the control group will be asked to refrain from using a VR modality intraoperatively. They will otherwise prepare for surgery and undergo perioperative care according to the current standard of care.

Follow Up

Postoperative care, including management in the PACU, will be conducted to the current standards of care. Data on postoperative outcomes, medications, and pain scores will be collected as indicated below in order to assess secondary outcomes.

After surgery, members of the study team will meet with the patient and ask them to complete a survey about their experience and overall satisfaction with the study. The survey will be built and administered using REDCap. If the patient is unable to complete the survey in-person, a link directly to the REDCap survey will be emailed to them.

Consistent with the current standard of care, patients will return to their surgeon's office for a postoperative visit, which typically occurs one month after surgery. Data from this visit, including surgical outcomes and assessment, will be passively abstracted from their medical record.

Data Collection

In order to assess our primary and secondary outcomes, data will be collected on intraoperative propofol dose, length of

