This study utilizes a non-invasive device therefore we expect the associated risks to be minimal. Potential risks of using virtual reality in this setting could include motion sickness, patient dissatisfaction, seizures and infection control concerns from shared equipment. To attempt to minimize the risk of motion sickness that can occur during virtual reality experiences, we have excluded patients with this known condition. Further, the anesthesia provider will be able to provide anti-emetics as prophylaxis or treatment based on their determination of clinical need. If a patient is dissatisfied with the VR experience during surgery, they will have the full ability to discontinue the intervention and receive standard anesthesia care at any time. Similarly, should the anesthesia provider determine that the clinical situation necessitates standard anesthesia practice, they will be able to discontinue use of the VR program at any time. Some people (about 1 in 4000) may have severe dizziness, seizures, eye or muscle twitching or blackouts triggered by light flashes or patterns, and this may occur while they are watching TV or experiencing virtual reality. This is most pronounced in children and the elderly. To mitigate this potential risk we are excluding children and patients with a history of seizures. If a patient experiences any symptoms the VR will be stopped and the patient will be treated accordingly. Lastly, to minimize the potential infection control risks from shared VR equipment, the primary investigator and the representatives from VR health have worked with the BIDMC infectious disease and infection control representatives to select equipment that can be wiped with sterilization wipes between uses. With the use of additional disposable barriers such as caps/hairnets, they are confident that the risk of transmission between subjects with the shared equipment to be minimal.

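### Adverse-event monitoring ends at PACU discharge, so a later headset-related infection would not be captured as an adverse event, and the one-month record is not used to look for it

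*Combined protocol and SAP*

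**What the plan says.** Three parts of the protocol bear on this.

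- **Section B3.A, Safety Monitoring and Reporting.** Reporting is limited to events attributed to the study procedures, serious or not; the second item reads "All non-serious Adverse Events believed to be related to the study procedures". The time limit follows: "Adverse events will be monitored until the time of PACU discharge". No type of event is exempted.
- **Section B5.** The risks are listed as "motion sickness, patient dissatisfaction, seizures and infection control concerns from shared equipment". The section then describes wiping the equipment between uses and adding disposable barriers, after consultation with infection control. Of those consulted it says "they are confident that the risk of transmission between subjects with the shared equipment to be minimal".
- **Section B3.A, Follow Up and Data Collection.** Patients return for "a postoperative visit, which typically occurs one month after surgery". The protocol adds: "Data from this visit, including surgical outcomes and assessment, will be passively abstracted from their medical record". Separately, the chart review covers "intraoperative vital signs, medication administration, and postoperative outcome data", with no end date given.

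No section connects the one-month data to adverse-event reporting, and none asks about infection of the eye or face.

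**The concern.** The monitoring window suits most of the listed risks. Motion sickness and seizures would be expected mainly while the headset is on, and dissatisfaction has its own survey. Infection differs: exposure ends in the operating room, but signs would be expected later. The one named risk most likely to need follow-up is the one the window fits worst.

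The equipment is shared, so a case in one participant also matters to the next person who wears the headset. With monitoring closed at PACU discharge, the team has no planned way of learning that the wipes and barriers had failed. The expectation of minimal transmission risk would go unchecked, and an adverse-event table with no infections would say nothing about infections that appeared later.

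**Working it through.** The plan gives no figure of its own on this point: no infection rate, no time to onset and no expected PACU stay (length of stay is a secondary outcome to be measured). The check is therefore mainly a comparison of sections, followed by arithmetic for scale.

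**Step 1. Each named risk against the window**

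| Risk in B5 | When expected (assumption) | Planned capture |
|---|---|---|
| Motion sickness | Mainly during headset use | Within the adverse-event window |
| Seizures | Mainly during headset use | Within the adverse-event window |
| Dissatisfaction | During or soon after surgery | Postoperative survey |
| Infection from shared equipment | Probably after PACU discharge | Not as an adverse event; incidental only |

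**Step 2. Is the cut-off justified?** The reason given in B3.A for narrowing the scope is that surgical patients may have unrelated health events in hospital. That supports restricting reports to related events, which the plan already does. It does not explain why a related event after PACU discharge should fall outside.

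**Step 3. Could a late case still reach the data?** Yes, by two routes: the abstracted one-month visit and the chart review of postoperative outcomes. Neither has an infection item, and neither feeds the adverse-event report. Capture by these routes would be unsystematic.

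**Step 4. What follow-up could show.** Inputs from B3.B: planned enrolment 40 at 1:1, so 40 / 2 = 20 wear the headset; before the dropout allowance, 32 / 2 = 16.

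If n headset patients are fully ascertained and none has an infection, the exact one-sided 95% upper bound on the rate is 1 − 0.05^(1/n).

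- n = 20: 1 − 0.05^(1/20) = 0.139, or 13.9%
- n = 16: 1 − 0.05^(1/16) = 0.171, or 17.1%
- n = 10, if only half of the 20 notes mention the eye or face (assumption): 1 − 0.05^(1/10) = 0.259, or 25.9%

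The chance of at least one case among 20 is 1 − (1 − p)^20. The rates below are assumed.

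| Assumed rate p | Chance of at least one case in 20 |
|---|---|
| 0.1% | 2% |
| 1% | 18% |
| 5% | 64% |
| 10% | 88% |

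Under the present window, any infection first appearing after PACU discharge is outside adverse-event capture whatever the value of p.

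**The case against.** The strongest reply is that the plan handles this risk by prevention. It excludes patients with open wounds or active infection around the face or eyes and those under droplet or airborne precautions. Equipment was chosen with infection control staff, is wiped between uses and is used with barriers. The device is non-invasive and worn for one procedure, the trial has 40 patients, and safety is neither an aim nor a listed endpoint. At rates of 0.1% to 1%, follow-up of 20 patients would show a case only about 2% to 18% of the time. Notes from a hand-surgery visit may also say nothing about the eye or face, so counting silence as absence would create false reassurance.

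Most of this stands as a limit on what the change can achieve. It does not explain why the one-month record, which is abstracted anyway, is left out of safety reporting for a risk that the protocol itself names. Prevention and detection also serve different purposes: only detection would show that prevention had failed.

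A reader might go further and infer that a headset infection can never be recorded, or that the trial is bound to report none whatever happens. The documents do not support that. The cut-off applies to adverse-event monitoring. The one-month abstraction and the chart review could still pick up a case, and nothing forbids reporting it. Nor does any section say that the trial will present an infection count or claim that the headset is safe.

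**Conclusion.** The concern holds in limited form. An infection appearing after PACU discharge would not be captured as an adverse event, and the abstracted one-month record is not used to look for it, although a case could surface incidentally. This rests on the assumption that onset would usually follow PACU discharge, which is plausible but not stated in the documents.

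The effect is confined to safety reporting for about 20 exposed patients. Randomisation, sample size, the primary analysis and the listed secondary outcomes are untouched. The gain from closing the gap is modest: the 13.9% bound is loose and needs complete ascertainment, which passive surgical notes may not provide. The change is worth making because it costs little and because the stated cut-off misses a risk that the plan itself lists.

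**What to change.** 1. In B3.A, keep PACU discharge as the end of monitoring for other events. Extend adverse-event capture for suspected device-related eye or face infection to the routine one-month visit.
2. Add one field to the existing one-month abstraction in both arms: eye or face infection, coded yes / no / not documented. Collecting it in controls gives a background count from patients who did not wear the headset.
3. Report all three categories by arm. Treat a blank or silent note as not documented, and base any upper bound only on patients with a documented answer.
4. State that suspected device-related cases found this way are reported as adverse events.

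If the investigators prefer the present cut-off, they should justify it and say in the trial report that later infection was not assessed.

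The cost is one abstraction field and a sentence or two of protocol text, with no extra visit or staff. The downside is incomplete information where the surgical notes are silent, which the third category makes visible.

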Data Analysis: Patients will be prospectively randomized using 1:1 block randomization of equal sizes. Analyses will be conducted using SAS version 9.3 (SAS Institute, Cary, North Carolina) or later. Descriptive statistics of the data will be performed. Continuous data will be represented using mean (\pm standard deviation) or median (interquartile range) for variables not normally distributed and compared using parametric or non-parametric t-tests as appropriate. Categorical data will be presented using proportions and compared using a chi-square or Fishers Exact test.

Primary Outcome

The primary outcome of this study is total intraoperative propofol dose, evaluated as a continuous variable. This will be assessed using a t test or Wilcoxon Rank Sum test, depending on the normality of the data. Although randomization should account for potential difference between groups, we will employ univariate and multivariable linear regression modeling to adjust for differences that persist, as necessary. Odds ratios and 95% confidence intervals will be reported. Our primary analysis will be conducted using intention to treat principles.

Secondary Outcomes

A priori secondary outcomes include length of PACU stay, postoperative analgesia dose requirements, postoperative pain scores, and overall patient satisfaction. Differences in time, medication administration and pain scores will be expressed as continuous variables. Patient satisfaction will be assessed from the REDCap survey, and will provide quantifiable estimates of satisfaction in multiple areas including but not limited to pain, anxiety, nausea, and overall experience. Adherence to the randomization assignment will be evaluated, and in the event that any patient receives an intervention different than their randomization assignment, we will also perform a per protocol analysis as an additional secondary outcome. For all secondary analyses, parametric or non-parametric tests will be employed in an analogous fashion to our baseline characteristics between groups.

C. Subject Selection

Inclusion Criteria:

1. Patients undergoing hand or wrist surgery at BIDMC under MAC

Exclusion Criteria:

1. Age < 18
2. Open wounds or active infection of the face or eye area
3. History of motion sickness
4. History of claustrophobia
5. History of seizures or other symptom linked to an epileptic condition
6. Patients who plan to wear hearing aids during the procedure

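### The sample size of 32 is the size for a 39% reduction in propofol dose, not the 50% reduction the protocol states

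*Combined protocol and SAP*

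**What the plan says.** The only statement of the assumed effect is in section B3, part B (Statistical Considerations), under Sample Size Justification. It sets the error rates ("Using a two sided α of 0.05, 80% power") and the inputs ("mean propofol doses of 0.069 (standard deviation 0.03) and 0.042 (SD 0.021"), and concludes "we anticipate needing to enroll a total of 32 patients", the purpose being "to be able to detect a 50% reduction in the mean total intraoperative propofol dose". It calls this effect reasonable because, in a related study, "investigators were able to demonstrate a >50% reduction in dose for major joint surgery". It then adds a dropout allowance: "enroll an additional 8 patients to bring the total planned enrollment to 40 patients, with 20 in each of the two groups".

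Allocation is 1:1 (section B3, part A, Study Procedures). The Primary Outcome paragraph gives the test: "This will be assessed using a t test or Wilcoxon Rank Sum test, depending on the normality of the data". No other section gives a different effect size or explains the 50%.

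**The concern.** The percentage and the two means are in the same sentence and do not agree. Either the percentage does not describe the calculation, or one of the means is wrong.

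This matters because it is the protocol's one statement of what the trial can detect on its primary outcome. A reader facing a non-significant result would take the design to have had 80% power against a 50% reduction. The justification is affected too: a result above 50% elsewhere is offered in support of an effect that the calculation did not use.

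**Working it through.** **Inputs**, all from the Sample Size Justification unless noted: two-sided α = 0.05; power 80%; means 0.069 and 0.042; SDs 0.03 and 0.021; 1:1 allocation (Study Procedures). The documents give no unit and do not say which mean belongs to which arm. I take the higher as control. The missing unit affects neither the ratio nor the sample size.

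**Step 1: the reduction implied by the means.**
- Difference: 0.069 − 0.042 = 0.027.
- Relative to the higher mean: 0.027 / 0.069 = 39.1%.
- Half of 0.069: 0.0345, not 0.042.
- Other denominators: 0.027 / 0.042 = 64.3% of the lower mean; 0.027 / 0.0555 = 48.6% of the average of the two means. The last is near 50%, but it is not a reduction in the mean.

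**Step 2: reproduce the stated 32.**

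Normal approximation: n per arm = (SD₁² + SD₂²)(z₀.₉₇₅ + z₀.₈₀)² / difference² = (0.0009 + 0.000441) × (1.960 + 0.8416)² / 0.027² = 14.4, so 15 per arm.

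Noncentral t: the noncentrality parameter is difference / √((SD₁² + SD₂²)/n). At n = 16 it is 0.027 / √(0.001341/16) = 0.027 / 0.00915 = 2.95.

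| n per arm | Power, pooled t | Power, Welch t |
|---|---|---|
| 15 | 78.7% | 78.4% |
| 16 | 81.4% | 81.1% |

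The smallest n reaching 80% is 16 per arm, or 32 in total. The plan's figure is reproduced exactly for a 39% reduction.

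**Step 3: what a 50% reduction would need.** The means are now 0.069 and 0.0345, a difference of 0.0345. The SD of the lower-dose arm under this effect is not given, so three values are assumed.

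| SD, higher / lower arm | n per arm for 80% power | Total | Power at 16 per arm |
|---|---|---|---|
| 0.03 / 0.021 (as stated) | 10 (pooled, 80.4%) or 11 (Welch, 84.0%) | 20 to 22 | about 95% |
| 0.03 / 0.03 | 13 | 26 | 88% |
| 0.03 / 0.015 (SD halves with the mean) | 9 | 18 | about 98% |

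None gives 32. If instead the lower mean is kept and the higher one is set to 0.084, so that 0.042 is half of it, the stated SDs need 8 per arm (pooled), or 16 in total, which is not 32 either.

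**Step 4: smallest reduction detectable with 80% power.** At 16 per arm with the stated SDs (pooled t), the smallest difference is 0.0265, and 0.0265 / 0.069 = 38.4%.

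**Step 5: dropout.** 32 / (1 − 0.20) = 40, so the step from 32 to 40 is consistent with 20% loss, although no rate is stated. It does not bear on the percentage.

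**The case against.** The best defence is that only a label is wrong. The α, power, means, SDs and sample size are all printed, agree with one another and reproduce 32. Anyone reading the sentence can work out 39%. Enrolment, allocation, outcome and test do not change.

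The error also runs in the safe direction. A 50% reduction needs fewer patients than planned. At the full 20 per arm, power for it would be about 98% with the stated SDs, or 94% with both SDs at 0.03. Sizing for 39% when a related study showed more than 50% is, if anything, the more cautious choice. Finally, a completed trial is better judged by its estimated difference and confidence interval than by its design effect.

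Most of this stands, and it limits the consequence: the trial is not underpowered for the effect it names. It does not remove the error. The stated effect contradicts the stated inputs, and the text alone cannot show whether the percentage or a mean is mistaken. Nor does the cited study directly support the effect that was used. The appeal to the confidence interval is weakened by the Primary Outcome paragraph, which attaches its intervals to odds ratios although the outcome is continuous.

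**Conclusion.** The statement is wrong as written. The plan's means are a 39.1% reduction, about 11 percentage points short of the 50% claimed, and 32 patients is the correct t-test sample size for that 39%. With 16 evaluable patients per arm, the design has about 81% power for 39% and about 95% for 50% (88% if both SDs are 0.03), not 80% for 50%.

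The 39.1% depends only on the two printed means. The power figures assume approximately normal doses, the stated SDs and a t test. If the Wilcoxon test is used instead, simulation with normal data gives about 78% power at 16 per arm and 81% at 17 for the stated means. That is a small shortfall and does not alter the finding.

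The harm is to the interpretation and justification of the trial, not to patient numbers.

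**What to change.** In the Sample Size Justification, replace the 50% with a 39% reduction (0.069 to 0.042, absolute difference 0.027) and keep 32 evaluable and 40 enrolled. Reword the comparison with the major joint surgery study to say that this trial is powered for a smaller effect than was seen there. The cost is one or two sentences, with no change in enrolment.

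If 50% was the intended target, the sponsor should reconcile the percentage with the means, give the source of the corrected inputs, and recalculate the sample size, or restate the power of 32 evaluable patients. The documents do not show which mean would be at fault, so that choice rests with the sponsor. In either case, giving the unit of the means and naming the arm for each would make the calculation checkable.
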